## 6.5.3. Intent to Treat Population

The intent to treat (ITT) population will include all randomized subjects, regardless of whether study treatment was administered. This population is the primary population for the analysis of the efficacy and health outcomes data. Data will be analyzed according to randomized treatment.

## 6.5.4. Per-Protocol Population

The per protocol (PP) population will include subjects in the safety population who complete Part 1. In addition, a decision will be made prior to database lock on which (if any) subjects are to be excluded from the PP population based upon major protocol deviations. In the PP analysis, subjects will be assessed based on the actual treatment received. The PP population may be used as a secondary population for efficacy analyses.

### 6.5.5. Completers

The subset of subjects in the ITT population who complete Part 1 of the study will comprise the completers population. The completers population will be used for a sensitivity analysis of the primary efficacy analysis for Part 1 only. Data will be analyzed according to randomized treatment.

### 6.5.6. Pharmacodynamic Population

The PD population will include all subjects for whom at least 1 pre- and post-dose plasma kallikrein inhibition result can be estimated. Data will be analyzed according to the actual treatment received. This population will be used for the listings and summaries of PD data.

## 6.5.7. Pharmacokinetic/Pharmacodynamic Population

The PK/PD population will include all subjects for whom at least 1 pre- and post-dose plasma kallikrein inhibition result can be estimated with a corresponding plasma BCX7353 concentration (placebo samples not analyzed will be assumed to have a zero concentration). This population will be used for plots comparing plasma kallikrein inhibition and plasma BCX7353 concentrations.

## 6.6. Baseline Definition

In general, the baseline value is the last available assessment prior to the time of first dose of study drug unless otherwise specified. For tables that include adjusted visit information, the baseline for active treatment for subjects who originally were assigned to placebo will be the last available assessment prior to the time of first dose of active treatment in Part 2, unless otherwise specified. The date and time of first dose of treatment in Part 2 is recorded in the eCRF at the Week 24 assessment.

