For tables produced by visit that combine active treatment data for those originally assigned to active treatment with those originally assigned to placebo there will be an adjusted visit that corresponds to the time since active dosing (either Day 1 for those originally assigned to active dose or Week 24 visit for those originally assigned to placebo; see Table 8). This will allow for combining data from active treatments in Part 1 (either 110 or 150 mg) with active treatment in Parts 2 and 3 that follows placebo (either 110 or 150 mg). The adjusted visit for those assigned to 110 or 150 mg in Part 1 will equal the original visit (ie, Day 1).

Original Visit	Adjusted Visit
Week 24	Day 1
Week 26	Week 2
Week 28	Week 4
Week 32	Week 8
Week 36	Week 12
Week 48	Week 24
Week 60	Week 36
Week 72	Week 48
Week 84	Week 60
Week 96	Week 72

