#### **10.4.** Laboratory Data

The following endpoint is a Part 1 safety endpoint and a primary endpoint for Parts 2 and 3:

• Number and proportion of subjects who experience a treatment-emergent Grade 3 or 4 laboratory abnormality

A listing of clinical laboratory evaluations is provided in the Protocol, Section 11.2.6.

Clinical laboratory assessments and corresponding changes from baseline will be summarized for each laboratory panel by treatment group and visit. Laboratory abnormalities will be graded according to the DMID Adult Toxicity Table (publish date: November 2007; see Protocol Appendix 16.1). Any graded abnormality that occurs following the initiation of study drug and represents at least 1-grade increase from the baseline assessment is defined as treatment emergent.

Urinalysis results will be summarized by treatment and visit and listed by subject and treatment.

The number and percentage of subjects experiencing treatment-emergent graded toxicities will be summarized. Treatment-emergent Grade 3 or 4 laboratory abnormalities will be summarized separately. Laboratory toxicity shifts from baseline to worst postbaseline assessments will be summarized.

The number and percentage of subjects who have post-baseline elevations in liver transaminase (alanine aminotransferase [ALT] or aspartate aminotransferase [AST]) or bilirubin abnormalities in relation to fold above the upper limit of normal will be summarized according to the FDA's Premarketing Clinical Evaluation on Drug-Induced Liver Injury Guidance for Industry (DHHS 2009).

The following categories of abnormal hepatic laboratory values will be evaluated for any occurrence among all post baseline assessments (where "and" indicates elevations occurring at the same visit). Within each treatment group and laboratory parameter grouping, a subject may be counted once per elevation criteria using the worst-case result. That is, a subject with a worst-case ALT elevation  $>3 \times$  the upper limit of normal (ULN) for a given treatment group would be counted once in the ALT  $> 1.5 \times$  ULN category and once in the ALT  $> 3 \times$  ULN category, regardless of how many ALT elevations the subject had that met the  $> 3 \times$  ULN and  $> 1.5 \times$  ULN elevation criteria.

- ALT and/or AST >  $3 \times$  ULN and total bilirubin > 1.5 or  $2 \times$  ULN
- AST > 1.5, 3, 5, 10, and 20 × ULN
- ALT > 1.5, 3, 5, 10, and 20 × ULN
- Total bilirubin  $> 1, 1.5, \text{ or } 2 \times \text{ULN}$

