#### **10.7. 12-lead Electrocardiograms**

Baseline (predose) and Week 24 ECGs will be obtained in triplicate (ie, 3 separate readings) at 1- to 5-minute intervals, with baseline values calculated from an average of the 3 readings. All other ECGs will be single assessments.

An ECG should be repeated for a change from baseline in corrected QT interval using Fridericia's method (QTcF) > 60 msec or a QTcF interval > 500 msec.

ECGs and corresponding changes from baseline will be summarized by treatment group and visit using descriptive statistics.

ECG findings will be summarized.

The change from baseline in QTcF will be determined by routine ECGs. At each time point where ECGs are analyzed, an individual subject's change from baseline will be calculated as:

 $\Delta ik = (QTcF \text{ for Subject i at Time Point } k - Baseline QTcF)$ 

QTcF measurements will be the average of triplicate ECGs at baseline and Week 24 and single values at all other time points.

A distribution plot of QTcF over time will be produced using the format recommended by the FDA/Industry/Academia Safety Graphics working group

(https://www.ctspedia.org/do/view/CTSpedia/StatGraphHome). The graph format to be used is the same as the graph provided for the distribution of ALT by time and treatment.

For routine ECGs, the number and proportion of subjects with  $QTcF \le 450$ , > 450 to  $\le 480$ , > 480 to  $\le 500$ , and > 500 msec; or changes of  $\le 30$ , > 30 to  $\le 60$ , or > 60 msec will be summarized. Unscheduled ECG results will be included in this summary table.

All ECG values and findings will be listed by subject, treatment, and visit.

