14.3.5.4.ES	Safety	Summary of Observed and Change from Baseline Laboratory Data: Additional Tests, Entire Study
14.3.5.5	Safety	Summary of Observed and Change from Baseline Laboratory Data: Continuous Urinalysis Parameters, Part 1
14.3.5.5.ES	Safety	Summary of Observed and Change from Baseline Laboratory Data: Continuous Urinalysis Parameters, Entire Study
14.3.5.6	Safety	Summary of Observed Laboratory Data: Categorical Urinalysis Parameters, Part 1
14.3.5.6.ES	Safety	Summary of Observed Laboratory Data: Categorical Urinalysis Parameters, Entire Study
14.3.5.7	Safety	Shift from Baseline to Worst Postbaseline Assessment: Clinical Chemistry, Part 1
14.3.5.7.ES	Safety	Shift from Baseline to Worst Postbaseline Assessment: Clinical Chemistry, Entire Study
14.3.5.8	Safety	Shift from Baseline to Worst Postbaseline Assessment: Hematology and Coagulation, Part 1
14.3.5.8.ES	Safety	Shift from Baseline to Worst Postbaseline Assessment: Hematology and Coagulation, Entire Study
14.3.5.9	Safety	Shift from Baseline to Worst Postbaseline Assessment: Urinalysis, Part 1
14.3.5.9.ES	Safety	Shift from Baseline to Worst Postbaseline Assessment: Urinalysis, Entire Study
14.3.5.10	Safety	Shift from Baseline to Worst Postbaseline Assessment: Additional Tests, Part 1
14.3.5.10.ES	Safety	Shift from Baseline to Worst Postbaseline Assessment: Additional Tests, Entire Study
14.3.5.11	Safety	Summary of Treatment-Emergent Graded Laboratory Abnormalities, Part 1
14.3.5.11.ES	Safety	Summary of Treatment-Emergent Graded Laboratory Abnormalities, Entire Study
14.3.5.12	Safety	Summary of Treatment-Emergent Grade 3 and 4 Laboratory Abnormalities, Part 1
14.3.5.12.ES	Safety	Summary of Treatment-Emergent Grade 3 and 4 Laboratory Abnormalities, Entire Study
14.3.5.13	Safety	Summary of Treatment-Emergent Laboratory Toxicity Grade Increases from Baseline, Part 1
14.3.5.13.ES	Safety	Summary of Treatment-Emergent Laboratory Toxicity Grade Increases from Baseline, Entire Study
14.3.5.14	Safety	Summary of Fold x ULN for Liver Function Tests, Part 1
14.3.5.14.ES	Safety	Summary of Fold x ULN for Liver Function Tests, Entire Study
14.3.5.15	Safety	Summary of Fold Change from Baseline for Liver Function Tests, Part 1
14.3.5.15.ES	Safety	Summary of Fold Change from Baseline for Liver Function Tests, Entire Study
14.3.5.16	Safety	Summary of Elevations in Post-baseline Liver Function Tests, Part 1
14.3.5.16.ES	Safety	Summary of Elevations in Post-baseline Liver Function Tests, Entire Study

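### Study 302 SAP: for subjects first randomized to placebo, the entire-study treatment-emergent laboratory and worst-value shift tables default to a pre-placebo baseline, so a grade rise that began on placebo can be counted under BCX7353

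*SAP*

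**What the plan says.** All references are to the Study 302 SAP unless stated otherwise.

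- **Default baseline (6.6).** "In general, the baseline value is the last available assessment prior to the time of first dose of study drug unless otherwise specified". Section 4.1 uses study drug to mean BCX7353 or placebo, so for a placebo subject the default is the value before the first placebo dose.
- **Exception (6.6).** The baseline moves to the last value before the first active dose in Part 2 for a limited class of display: "For tables that include adjusted visit information, the baseline for active treatment for subjects who originally were assigned to placebo".
- **Where adjusted visits are used (6.1).** "For tables produced by visit that combine active treatment data for those originally assigned to active treatment with those originally assigned to placebo". Table 8 then maps Week 24 to adjusted Day 1.
- **Treatment-emergent laboratory abnormality (10.4).** A graded abnormality after study drug starts qualifies if it "represents at least 1-grade increase from the baseline assessment is defined as treatment emergent". No treatment period is named.
- **Shift tables (10.4).** "Laboratory toxicity shifts from baseline to worst postbaseline assessments will be" summarized, with no mention of visit.
- **By-visit summaries.** For laboratory data (10.4): "Clinical laboratory assessments and corresponding changes from baseline will be summarized for each laboratory panel by treatment group and visit". For ECGs (10.7): "ECGs and corresponding changes from baseline will be summarized by treatment group and visit using descriptive statistics".
- **Output list (17.1).** Table 14.3.5.12.ES is the "Summary of Treatment-Emergent Grade 3 and 4 Laboratory Abnormalities, Entire Study". Tables 14.3.5.7.ES to 14.3.5.10.ES are the worst-postbaseline shifts.
- **Columns (6.1, Table 7).** Active-treatment data from former placebo subjects go into the after-placebo column for their dose, the pooled column for that dose and the all-active column. The placebo column holds Part 1 data only.

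**The concern.** For former placebo subjects, a count reported under BCX7353 should compare values on BCX7353 with the value just before BCX7353 was started. With a Day 1 baseline, 24 weeks of placebo lie between the baseline and the first active dose. Two errors follow:

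- A grade increase that arose on placebo and is still there at a Part 2 or 3 assessment meets the definition again. It is counted once under placebo for Part 1 and once more under active drug.
- If the grade was higher on Day 1 than at Week 24, a return to the Day 1 grade on drug shows no increase and is missed.

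The treatment-emergent Grade 3 or 4 laboratory abnormality is a primary endpoint of Part 2 (3.2.6) and Part 3 (3.2.8). The by-visit tables for the same subjects use the later baseline, so two tables in one report could describe the same data differently.

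**Working it through.** The SAP gives no figure on this point, so the check is one of text followed by a size calculation.

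**Step 1. Which baseline each entire-study display receives for former placebo subjects**

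| Display | Described as by visit? | Baseline that follows |
|---|---|---|
| Laboratory change from baseline (10.4) | Yes | Before first active dose |
| ECG and QTcF change summary (10.7) | Yes | Before first active dose |
| Treatment-emergent graded laboratory tables, including 14.3.5.12.ES | No | Day 1, by default |
| Worst-postbaseline shifts, 14.3.5.7.ES to 14.3.5.10.ES | No | Day 1, by default |
| QTcF change categories, 14.3.7.3.ES | Not stated | Unspecified |
| Fold change in liver tests, 14.3.5.15.ES | Not stated (title only) | Unspecified |
| Treatment-emergent adverse events (10.1) | Not relevant: assigned by when the event began | Unaffected |
| All Part 1 tables | Not relevant: Part 1 treatment only | Unaffected |

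**Step 2. What the two baselines do to a single subject** (invented grades; increase = worst grade on drug minus baseline grade)

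| Day 1 | Week 24, on placebo | Worst on drug | Increase from Day 1 | Increase from Week 24 | Result under the default |
|---|---|---|---|---|---|
| 0 | 3 | 3 | 3 − 0 = 3 | 3 − 3 = 0 | Counted under BCX7353, though it arose on placebo |
| 3 | 1 | 3 | 3 − 3 = 0 | 3 − 1 = 2 | Missed, though it worsened on BCX7353 |
| 0 | 0 | 3 | 3 | 3 | Same either way |

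A rise that resolves before the first active dose and does not recur stays in the placebo column and does no harm.

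**Step 3. Column sizes**

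- Placebo subjects: 40 (technical summary and 4.3.1). Re-randomized 1:1 (4.4.2): 40 / 2 = 20 per dose.
- If 20% leave before Part 2 (the dropout allowance in 4.3.1): 40 × 0.8 = 32, and 32 / 2 = 16 per dose.
- Pooled dose column: 40 + 20 = 60, or 40 + 16 = 56. The 40 subjects originally on that dose stay in the denominator once dosed.

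**Step 4. Effect of one misattributed subject**

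- After-placebo column: 1/20 = 5.0%; 1/16 = 6.3%.
- Pooled dose column: 1/60 = 1.7%; 1/56 = 1.8%.

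**Step 5. How many there might be.** The documents give no rate. Let q be the share of former placebo subjects with a graded rise over Day 1 that is still present in Part 2. The range for q is an assumption and covers abnormalities of any grade. With n = 20, the expected number is 20q, the chance of at least one is 1 − (1 − q)^20, and the excess in the pooled dose column is 20q/60.

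| q (assumed) | Expected number per after-placebo column | Chance of at least one | Excess in pooled dose column |
|---|---|---|---|
| 0 | 0 | 0 | 0 |
| 2.5% | 0.5 | 0.40 | 0.83 points |
| 5% | 1 | 0.64 | 1.67 points |
| 10% | 2 | 0.88 | 3.33 points |
| 20% | 4 | 0.99 | 6.67 points |

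With the pre-active baseline, misattribution of this kind is zero for every q. The table covers the overcount only. The missed worsenings run the other way and are not quantified here.

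**The case against.** The strongest reply is that this is an ambiguity, not an instruction. The default in 6.6 is hedged, nowhere does the SAP say that these tables use Day 1 for former placebo subjects, and mapping Week 24 to adjusted Day 1 suggests that a pre-active baseline was in mind. The table shells are in a separate document, and the Study 302 protocol, which might define treatment emergence, was not supplied. The safety analyses are descriptive, and no hypotheses are tested in Parts 2 and 3. The summaries by multiple of the upper limit of normal need no baseline, and the listings show every Grade 3 or 4 value.

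Part of this stands. The Day 1 baseline follows from a default that nothing overrides, not from an explicit statement. The listings and the multiples of the upper limit would let a careful reader spot a problem. But the default is written down, its exception is tied to a class of table that these do not fit, and the by-onset rule in 10.1 covers adverse events only. Descriptive use does not make a count correct. Two programmers could also read 6.6 differently and report different values for a primary endpoint.

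A reader might infer that QTcF change is generally judged against the pre-placebo value. The text does not support that: the QTcF change summary is by visit and is reset. Only the categorical table is left open, as is the fold-change table.

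The Study 202 protocol (13.3.4) ties the laboratory baseline to the treatment period. It belongs to a different trial with a sequence design, so it shows that such wording was available but does not govern Study 302.

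**Conclusion.** The point holds for the entire-study treatment-emergent graded laboratory tables and the worst-postbaseline laboratory shift tables. As written, they default to a pre-placebo baseline for data reported under BCX7353. The error can go in either direction.

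Each misattributed subject moves an after-placebo column by 5.0 to 6.3 points and a pooled dose column by 1.7 to 1.8 points. These figures assume 40 placebo subjects, an even split, and between none and 20% lost before Part 2. The number of such subjects is unknown. For Grade 3 or 4 it is likely to be small, because the abnormality must arise on placebo and persist past the first active dose.

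It would be tempting to conclude that the Grade 3 or 4 counts will be materially inflated. The documents do not support that: they give no rate, and the range of q above is assumed and concerns any grade. The case for the change is that a primary safety endpoint should have one correct and unambiguous baseline. Part 1 results, adverse-event tables and the by-visit laboratory and QTcF change summaries are not in question.

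**What to change.** In 6.6, state that for all safety displays of active-treatment data, whether or not by visit, the baseline for subjects first randomized to placebo is the last assessment before the first active dose in Part 2. Name the displays: laboratory treatment emergence, shifts, fold changes and QTcF change categories. State also that treatment emergence for these data is judged from that dose. Cross-refer to this sentence in 10.4 and 10.7.

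Limit the change to safety. Section 8.7.1 already plans a separate AE-QoL change from Week 24 for these subjects, and a rule covering every display would cut across it. Leave the efficacy and AE-QoL baselines as specified.

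The cost is one sentence, two cross-references and one derived baseline flag. No new data are needed: Week 24 laboratory tests and triplicate ECGs are already scheduled (Table 2), and 6.6 says that the date and time of the first Part 2 dose are recorded.

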## 6.6.1. Baseline Attack Rate

Enrollment into treatment groups is stratified by the baseline HAE attack rate as determined by the IXRS system based on the number of attacks and duration of screening as input by the sites ( $\geq 2$  attacks/month vs. < 2 attacks/month). For analysis purposes, the baseline attack rate will be calculated from the diary data and expressed as attacks per month where 1 month = 28 days as follows:

Number of HAE attacks meeting baseline criteria from Screening to First Dose Date/time × 28

Date of First Dose – Screening Date + 1

Criteria that must be met for attacks to qualify for confirmation by the Investigator during the baseline period are provided in Section 4.1.

Baseline attack rate will be included in statistical models as appropriate.

### 6.6.2. Categorized Baseline Attack Rate

Categorized baseline attack rate refers to the categorization of the calculated baseline attack rate into strata ( $\geq 2$  attacks/month vs < 2 attacks/month).

### 6.6.3. Baseline Age

Age at time of consent is collected on the demographics form. This will be the baseline age for analyses and for determination of whether the subject is classified as an adult ( $\geq$  18 years) or an adolescent (12 to 17 years).

# 6.7. Derived and Transformed Data

## 6.7.1. Study Day

In this study, it is possible that the randomization date and date of first dose could differ. Study Day 1 is defined as the date of first dose.

If the date of measurement for a particular endpoint occurs on or after the first dose date, then study day will be calculated as:

(date of measurement - date of first dose) + 1

If the date of measurement occurs prior to the first dose date then study day will be calculated as:

date of measurement - date of first dose

There is no Day 0.

#### 6.7.2. Change from Baseline

Change from baseline is calculated as:

#### post baseline result – baseline result

Percent change from baseline is calculated as:

#### (change from baseline $\div$ baseline result) $\times$ 100

If either the baseline or the post-baseline result is missing, the change from baseline and/or percentage change from baseline is set to missing as well.

#### 6.7.3. Visit Windows

For summary purposes in general, records will be assigned to the scheduled visit collected on the case report form (CRF). Unscheduled and early termination visits will be assigned to an analysis window according to the study day of the actual visit date using the visit windows displayed in Table 9. All information collected at an unscheduled visit will be identified as such in the listings.

Visit	Relative Target Day	Protocol-Specified Visit Window	Analysis Visit Window
Screening visit	-14 to -56	-70 to -14	-70 to -14
Baseline	1	1	1
Week 2	15	13 to 17	2 to 22
Week 4	29	27 to 31	23 to 43
Week 8	57	55 to 59	44 to 71
Week 12	85	83 to 87	72 to 106
Week 18	127	125 to 129	107 to 148
Week 24	169	169	149 to 176
Week 26	183	181 to 185	177 to 190
Week 28	197	195 to 199	191 to 211
Week 32	225	223 to 227	212 to 239
Week 36	253	251 to 255	240 to 295
Week 48	337	330 to 343	296 to 373
Week 60	421	415 to 427	374 to 463
Week 72	505	499 to 511	463 to 547
Week 84	589	583 to 595	548 to 631
Week 96	673	664 to 680	≥632

Table 9:Visit Windows (Days)

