- Study drug should be taken at approximately the same time each day, with whichever meal is typically the largest of the day. Subjects are not required to take their doses at clinic visits. Subjects will take study drug in Part 1 beginning on Day 1 and will complete Part 1 dosing on Study Day 168 (day before Week 24 visit). Subjects will take Part 2 active study drug no sooner than the conclusion of the Week 24 visit on Study Day 169, after all other study procedures have been completed.
- The Investigator (or designee) will review the e-diary record of all HAE attacks that occur from Screening through Week 48 and either confirm or reject the attack as an HAE attack. At least 2 attacks that occur during the run-in period must meet the requirements outlined in Footnote 'n' in order to qualify the subject to randomize in the study. For all attacks that occur, subjects will be contacted within approximately 2 business days of the end of the attack to discuss the clinical characteristics of the attack, any questions the Investigator has on the entered data or to gain additional attack details not included in the e-diary that the Investigator deems important to clinically evaluate the event, as applicable. This information, in conjunction with the e-diary record, will be used by the Investigator to verify or reject the event recorded in the diary as an HAE attack. The e-diary data review, subject contact summary, and Investigator verification of the attack will be documented in the source records; the Investigator attack verification (confirmed or rejected) will also be recorded.
- y PK and PD blood samples will be drawn on all subjects with no particular relationship to the timing of study drug dosing. The Investigator (or designee) must ensure that the time of the last dose prior to PK and PD draw is recorded in the subject's e-diary (this may also be captured in the CRF).

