#### 6.7.4. Multiple Assessments

Where multiple planned scheduled measurements are recorded for a given time point (eg, electrocardiograms [ECGs]), the mean of the measurements will be calculated and used in any derivation of summary statistics. All available data will be listed.

When multiple visits occur within the same window, the scheduled visit will be used in analysis if available. If no scheduled visit occurs within the window and an unscheduled visit(s) and/or early termination visit occur within the window, the analysis visit closest to the target day will be selected for use in analysis. If deemed appropriate by the Sponsor (eg, in the case of a retest), unscheduled visits may be chosen for analysis given documentation of the desired visit from the Sponsor. Results from unscheduled visits will be eligible for inclusion in analyses of worst post-baseline results. Listings will display all visits as recorded on the CRF, including the date and study day. All available data including any totals, domains, or subscales of scale assessments summarized will be listed.

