# 8.6. Analysis of the Primary Efficacy Endpoint

## 8.6.1. Primary Efficacy Analysis

The primary efficacy endpoint for Part 1 of the study is the rate of investigator-confirmed HAE attacks during dosing in the entire 24-week treatment period during Part 1 (Day 1 to first dose of Part 2). The first dose in Part 2 is expected on Day 169. The primary efficacy analysis will be produced using the ITT population. The estimand will be based on data from subjects who are on study treatment and this analysis will not include data post treatment discontinuation.

The number of investigator-confirmed HAE attacks for Part 1 will be analyzed by treatment group using appropriate descriptive statistics for the confirmed attack rate (expressed as attacks/month) based on the 24-week dosing period or until study treatment discontinuation, if applicable. An additional summary of confirmed attack rate by month, including change from baseline attack rate and percentage change from baseline attack rate by month, will be produced. The primary efficacy analysis will be conducted using Part 1 data and the primary efficacy endpoints will be summarized and listed by Part 1 treatment group.

The attack rate and the treatment comparisons between each BCX7353 dose and placebo in the rate of investigator-confirmed HAE attacks during the Part 1 dosing period will be analyzed using a Poisson regression model. The number of investigator-confirmed attacks will be included as the dependent variable, the treatment will be included as a fixed effect, the stratification variable (baseline attack rate) will be included as a covariate and the logarithm of duration on treatment will be included as an offset variable. The estimated rate of attack for each treatment group, the treatment differences expressed as the attack rate ratio (BCX7353 over placebo rate ratio) and their associated 95% confidence intervals (CIs) will be provided from the Poisson regression model. The percentage reduction from placebo will be calculated for each dose as:

Rate reduction = 
$$1 - \text{attack rate ratio} = 1 - \frac{R_A}{R_P}$$

Where  $R_P$  is the estimated attack rate for Placebo treatment and  $R_A$  is the estimated attack rate for Active treatment.

Example SAS pseudo-code for the Poisson regression analysis is as follows:

```
proc genmod data = datasetname;
class trt01p catblatk/param=glm;
model icattacks = trt01p catblatk /dist=poisson link=log offset=logdurtrt;
run;
```

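### For unscheduled and early termination visits, SAP Table 9 assigns Day 463 twice, breaks its own spacing at Week 48/60, and runs Week 24 past the start of Part 2 dosing

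*SAP*

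**What the plan says.** Section 6.7.3 of the SAP leaves scheduled records under the visit on the case report form. The rest go through Table 9: "Unscheduled and early termination visits will be assigned to an analysis window according to the study day of the actual visit date". Under Section 6.7.1 "Study Day 1 is defined as the date of first dose", so the count runs from the first Part 1 dose and does not restart in Part 2.

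The analysis windows at issue are Week 24 (149 to 176), Week 26 (177 to 190), Week 48 (296 to 373), Week 60 (374 to 463) and Week 72 (463 to 547).

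On the change of treatment, a footnote to Table 2 says "Subjects will take Part 2 active study drug no sooner than the conclusion of the Week 24 visit on Study Day 169", and Section 8.6.1 says "The first dose in Part 2 is expected on Day 169". Section 15 records that Part 1 ends at the first Part 2 dose.

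For displays that pool active-drug data from both randomizations, Section 6.1 says "there will be an adjusted visit that corresponds to the time since active dosing". Table 8 turns Week 24 into Day 1 and Week 26 into Week 2 for subjects who came from placebo. Section 6.6 sets their active-treatment baseline as "the last available assessment prior to the time of first dose of active treatment in Part 2, unless otherwise specified".

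Section 6.7.4 settles competition within a window: "When multiple visits occur within the same window, the scheduled visit will be used in analysis if available". Failing that, the visit nearest the target day is used. The Sponsor may also select an unscheduled visit, for instance a retest, if the choice is documented.

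**The concern.** A windowing table should place each study day in exactly one visit, follow one rule, and not carry results across a change of treatment. Table 9 fails each test once.

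The third failure is the substantive one. Adjusted visits exist to line up subjects by time on active drug. A subject on active drug from Part 1 has days 2 to 8 of dosing filed under Week 2. A former placebo subject has the same days of dosing filed under adjusted Day 1, the pre-active visit. In Part 1 displays the same record would sit under placebo at Week 24, unless the program first cuts the data at the Part 2 dose. Section 15 implies such a cut, but Table 9 does not apply one.

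The first two failures leave filing to program order or to an unexplained boundary. Section 6.1 says that outside statisticians should be able to replicate the analyses.

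**Working it through.** **Inputs.** Target days and analysis windows come from Table 9. The start of Part 2 drug (Day 169) comes from the Table 2 footnote and Section 8.6.1. The adjusted-visit mapping comes from Table 8.

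**Step 1: recover the table's rule.** The SAP states none. Try: upper limit = (target + next target) / 2, with the next window starting one day later.

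| Boundary | Midpoint | Printed upper / next lower |
|---|---|---|
| Week 2/4 | (15+29)/2 = 22 | 22 / 23 |
| Week 4/8 | (29+57)/2 = 43 | 43 / 44 |
| Week 8/12 | (57+85)/2 = 71 | 71 / 72 |
| Week 12/18 | (85+127)/2 = 106 | 106 / 107 |
| Week 18/24 | (127+169)/2 = 148 | 148 / 149 |
| Week 24/26 | (169+183)/2 = 176 | 176 / 177 |
| Week 26/28 | (183+197)/2 = 190 | 190 / 191 |
| Week 28/32 | (197+225)/2 = 211 | 211 / 212 |
| Week 32/36 | (225+253)/2 = 239 | 239 / 240 |
| Week 36/48 | (253+337)/2 = 295 | 295 / 296 |
| Week 48/60 | (337+421)/2 = **379** | **373 / 374** |
| Week 60/72 | (421+505)/2 = 463 | 463 / **463** |
| Week 72/84 | (505+589)/2 = 547 | 547 / 548 |
| Week 84/96 | (589+673)/2 = 631 | 631 / 632 |

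The rule reproduces 13 of 14 upper limits, and 12 of 14 boundaries in full.

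**Step 2: Day 463.** It is 463 − 421 = 42 days from the Week 60 target and 505 − 463 = 42 days from the Week 72 target. The nearest-target rule in Section 6.7.4 chooses among visits inside one window, and here the distances tie anyway. Day 463 is the only day from 2 to 699 that falls in two windows, and no day in that range is left out.

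**Step 3: Days 374 to 379.** Day 374 is 37 days from Week 48 and 47 from Week 60. Day 378 is 41 and 43. These five days are strictly nearer Week 48 but are filed as Week 60. Day 379 is a tie (42 and 42), which the table gives to the earlier visit elsewhere.

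**Step 4: overlap with Part 2 dosing.** 176 − 169 = 7 days, Days 170 to 176. Counted from the first active dose, these are days 170 − 169 + 1 = 2 to 176 − 169 + 1 = 8. In Part 1, days 2 to 8 fall in Week 2 (2 to 22). For a former placebo subject they fall in Week 24, which is adjusted Day 1.

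**Step 5: what happens to such a record.** If the scheduled Week 24 visit is available it takes precedence, and the on-drug result leaves the by-visit table. If the scheduled assessment is missing, or the Sponsor selects the unscheduled one, an on-drug value represents the pre-active visit.

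**Step 6: protocol-window column.** Table 9 prints 330 to 343 for Week 48 and 664 to 680 for Week 96. Tables 3 and 4 give Day 337 + 7 (337 to 344) and Day 673 + 7 (673 to 680). Reading the plus as plus-or-minus gives 330 to 344 and 666 to 680, which do not match either.

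**The case against.** The best defence is that little passes through this table. Only unscheduled and early termination records are windowed, and no scheduled visit falls on Days 170 to 176 (Week 26 is Days 181 to 185). That stands, and it rules out several stronger readings.

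- A reader might infer that the former placebo group's baseline is contaminated. Section 6.6 cuts it at the time of the first active dose, so it is not.
- A reader might infer that early liver, ECG or rash signals are lost. Section 6.7.4 makes unscheduled results eligible for worst post-baseline analyses. Section 10.4 counts hepatic elevations at any post-baseline assessment, and Section 10.7 includes unscheduled ECGs in the QTcF categories. Section 10.1 assigns adverse events by onset. Listings show every visit with its date and study day. The documents do not show that such findings cluster at these visits.
- A reader might take all subjects, or the roughly 40 planned for placebo, as the number affected. Subjects on active drug since Part 1 change nothing on Day 169. What matters is the number of former placebo subjects with an unscheduled or early termination visit in that week, which the documents do not give.

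It can also be said that Week 24 is faulted for following the midpoint rule and Week 48 for breaking it. These are separate faults: a midpoint is reasonable between visits on one treatment, but not across a switch. It is also fair that the midpoint rule is inferred and that Day 379 alone is a tie.

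Finally, moving Days 170 to 176 to Week 26 cures only part of the problem. A continuing subject's unscheduled liver test would still yield to the scheduled Week 26 liver tests. The move helps early terminations and tests not scheduled at Week 26, and it stops on-drug values from standing for the pre-active visit.

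**Conclusion.** Table 9 is wrong as written in three places, all within its limited scope. One day (463) is assigned twice with nothing to resolve it. Five days (374 to 378) go to the farther visit, or six depart from the table's apparent rule if the tie on Day 379 is counted. About seven days of Part 2 dosing are filed under the Week 24 visit, which matters for subjects switching from placebo.

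The seven-day figure assumes that the Week 24 visit and first Part 2 dose fall on Day 169 as planned; a later dose shortens the overlap. The midpoint rule is inferred from the table's other boundaries. The consequence is confined to by-visit summaries, and probably to few records. The primary endpoint, baseline, worst post-baseline, QTcF-category and adverse event analyses do not depend on these windows. The mismatch in the protocol-window column is a matter of consistency only, because that column assigns no records.

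The SAP supplied is for study BCX7353-302 and the protocol is for BCX7353-202, so Table 9 could be tested only against the SAP's own text. The contradictions are internal to that text.

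**What to change.** Amend the analysis-window column of Table 9 before programming:

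- **Week 24 and Week 26.** For subjects who take a Part 2 dose, end Week 24 at the time of that first dose, and run Week 26 from after it to Day 190. For subjects with no Part 2 dose, keep Week 24 to Day 176.
- **Week 48:** 296 to 379. **Week 60:** 380 to 463. **Week 72:** 464 to 547.

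No separate windowing on adjusted study day is needed. Table 8 already sends Week 26 to adjusted Week 2, and with a Day 169 dose the new Week 26 window covers active-dosing days 2 to 22 (190 − 169 + 1 = 22), the same as Week 2 in Part 1. Windowing on adjusted day would also create a Week 18 window, for which the note to Table 8 says Part 2 has no visit.

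As a minor item, reconcile the protocol-window entries for Week 48 and Week 96 with Tables 3 and 4.

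The cost is five analysis-window cells, the sentence distinguishing subjects with and without a Part 2 dose, and two protocol-window cells. It needs no new data and does not change the primary analysis.
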